We propose a prospective, open-label, single-arm pilot study treating 40 subjects to assess the hypothesis that P2Y12 inhibition with Brilinta/ticagrelor (90 mg PO twice a day) reduces episodic and/or chronic migraine headache symptoms in patients with right to left shunt. There will be no randomization or blinding of therapy. The study drug will be provided, free of charge, by the manufacturer, Astra-Zeneca. All subjects will be treated with the same medical regimen, and will be treated at Columbia University Medical Center or one of Principal Investigators external offices. All subjects will have an initial visit that will include the completion of a screening questionnaire (inclusion/exclusion criteria), informed consent, transcranial Doppler screening, laboratory blood testing by venipuncture (approximately 15 cc of blood = 1 tablespoon), and instruction on the use of the daily headache log (see Appendix 1, Appendix 2). Over the next 28 days, the subjects will receive an e-mail/text reminder daily with a link to complete the headache log (see below). At a second study visit, following completion of the first baseline month, the study staff will review the subject's headache log material, will release those subjects with insufficient headache days in the screening month, will assign the remaining/eligible subjects to either the episodic or chronic migraine cohort, will distribute the study drug, will administer the Brilinta/ticagrelor loading dose, and will review the medication's proper use. After 7 days of treatment with Brilinta/ticagrelor, while still on therapy, subjects will be sent for additional laboratory testing (PRU test < 10 cc of blood by venipuncture). At the completion of the 28 days (+7 days) on Brilinta/ticagrelor, each subject will have a follow-up study visit within 7 days, before discontinuing medication. At the third study visit, headache logs will be reviewed with the study staff, results will be discussed, remaining medications and empty bottles will be returned, and adverse events will be reviewed. Headache frequency while on Brilinta/ticagrelor will be compared with the documented baseline for each subject. If the Brilinta/ticagrelor therapy was effective (> 50% reduction in monthly headache days), the subject could elect to continue therapy for an additional two months, while continuing to complete daily headache logs.

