Non-serious Adverse Event: any other adverse event that does not meet criteria for a serious adverse event.

Definitions of bleeding events are based on the PLATO Trial protocol²⁸, a previously published study comparing Brilinta/ticagrelor to clopidogrel.

- **Major Life-Threatening Bleeding** includes:
 - Any Fatal Bleed
 - Intracranial Hemorrhage
 - Intrapericardial bleed with cardiac tamponade
 - Bleeding resulting in hypovolemic shock or severe hypotension that requires pressors or surgery
 - Clinically overt or apparent bleeding associated with decrease in hemoglobin >5 g/dL
 - Bleeding requiring transfusion of ≥4 U whole blood or PRBCs
- **Other Major Bleeding** includes:
 - Bleed causing clinically significant disability (e.g., intraocular bleed with permanent vision loss)

- Clinically overt or apparent bleeding associated with decrease in hemoglobin >3 g/dL, but < 5 g/dL
 - Bleeding requiring transfusion of ≥ 2 , but < 4 U whole blood or PRBCs
- **Minor Bleeding** includes any bleeding requiring medical intervention but not meeting the criteria for major bleeding

Working Study Definitions:

- **Migraine Headache Day:** any study day in which headache symptoms occur. If a single headache lasts from the end of a calendar day into the beginning of the next, it would be considered a single headache day provided the event lasted less than 24 hours. If headache symptoms last more than 24 hours, it would be considered 2 Headache Days; more than 48 hours would be considered to be three days, etc. Aura alone ("Acephalic migraine") will not be considered a headache. The subject must experience headache pain.
- **"Responder" to Therapy:** $\geq 50\%$ reduction in the average number of monthly headache days during the month of therapy compared with participant's own baseline.
- **"Non-responder" to Therapy:** $< 50\%$ reduction in the number of monthly headache days during the month of therapy compared with participant's own baseline.
- **Platelet Inhibition:** This is a functional definition based on Platelet Reactivity. PRU Test Result (VerifyNow PRU Test, Accumetrics Inc. San Diego CA) of < 140 , while on therapy, will be considered a "positive" inhibitory effect of the medication. PRU results of $141 - 160$ will be considered a borderline response. PRU results > 161 will be considered a negative response.

Primary Study Endpoints:

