- Primary Efficacy Endpoint: A subject will be considered to have achieved the primary efficacy endpoint (a "Responder") if she/he has $\geq 50\%$ reduction in the number of monthly headache days during the month of therapy compared with participant's own baseline. If there is $< 50\%$ reduction in the number of migraine days, she/he will be considered a Non-Responder.
- Primary Safety Endpoint: Major bleeding episode (as defined above) or other life-threatening adverse event (see below), while taking the Brilinta/ticagrelor.

Secondary Study Endpoints:

- Secondary Efficacy Endpoints will be assessed as follows:
 - Absolute reduction in headache days as a continuous response variable.
 - Absolute reduction in headache intensity as a continuous response variable.

- Quantitative comparison of the number of monthly uses of rescue medications in the roll-in versus the treatment phase
- Comparison of time to headache resolution after rescue medications. If < 2 hours to resolution, will be considered a “successful” intervention. Will compare the percentage of successful interventions in the baseline and treatment phases.
- Secondary Safety endpoints: Non-life threatening adverse events to Brilinta/ticagrelor, including:
 - Minor bleeding
 - Allergic reactions
 - Shortness of Breath
 - Rash
 - Extreme fatigue
 - Any other symptom requiring the participant to withdraw from the study prior to completion of the one month medication administration

Subject Recruitment, Eligibility and Screening:

Study subjects will be recruited from hospital-based cardiology and headache clinic at Columbia University Medical Center, and through the private offices of the study physicians.

Preliminary Inclusion Criteria:

- Subject age 18 – 65 years
- Symptoms meet International Headache Society Criteria for Episodic Migraine or Chronic Migraine
- At least one year history of Episodic or Chronic migraine headache symptoms
- At least 6 headache days per month
- Subject agrees to use two forms of birth control or abstinence throughout duration of the study
- Subject able to complete online daily headache log
- Right to left shunt >grade 1 as determined by Transcranial Doppler evaluation

Preliminary Exclusion Criteria:

- Inability to understand the study or history of non-compliance with medical advice
- Currently taking a P2Y12 inhibitor
- Known hypersensitivity to Brilinta/ticagrelor
- History of stroke/transient ischemic attack (TIA) in the previous 6 months

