Baseline-Monitoring Phase (Phase 1): The subject will track her/his headaches daily for 28 days through an online survey tool (REDCap, licensed through Columbia University), to establish a baseline headache frequency. Each day, the subject will receive a text message/e-mail reminder to complete the daily headache log. The message will contain a link to log into the survey tool. During this phase, subjects will answer questions including presence or absence of headache symptoms, severity of headache symptoms, duration of symptoms, impact on daily activities, and use of rescue medication. Any headache lasting more than 24 hours will be counted as a second headache day. After 28 days of monitoring, the study coordinator will assess the subject's data to make sure the subject meets criteria for minimum headache days, and has been consistently performing the daily log. If the number of headache days is insufficient, the subject's participation will be completed. If the subject logs at least 6 headache days in the month, she/he will continue in the study. If the participant has been assigned to the Episodic arm of the study, but has >14 headache days in the screening month, or if the participant has been assigned to the Chronic arm of the study, but has <15 headache days in the screening month, she/he will NOT be reassigned, but will remain in the assigned group for analysis. The subject will then be treated with Brilinta/ticagrelor for a 28-35 day test period (Phase 2). The length of the test period will depend on the timing of the participant's follow-up visit after beginning treatment. The protocol window is 28+7 days.

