Treatment Phase (Phase 2): The subject will return for a follow-up visit to receive her/his medication within 1 week of completing the 28 day headache log. A loading dose of Brilinta/ticagrelor 180 mg will be administered in the office. Thereafter, for 28-35 days, a Brilinta/ticagrelor 90 mg tablet will be taken once in the morning and once in the evening, as close to 12 hours apart as possible. Each day, the subject will receive a text message reminder to login to the website, to record her/his headache activity. If she/he fails to login for two consecutive days, the study coordinator will place a follow-up phone call. PRU testing will be done a minimum of 7 days after the initiation of treatment, but before the medication is completed. A follow-up visit will be arranged between day 28 and day 35 days of monitoring to review efficacy, compliance, and side effects, to return unused medication, and to allow continued access to Brilinta/ticagrelor if indicated. A second Quality of Life survey will be completed.

Continued Access Phase (Phase 3): If the subject has a beneficial response to the Brilinta/ticagrelor (> 50% reduction in the average number of monthly headache days compared with the baseline), she/he will be offered continued access to the medication to complete an additional 2 months of therapy with on-going headache monitoring. A final office visit and Quality of Life Survey will be completed within 7 days of the 56th day of Phase 3 for return of unused medication, empty medication bottles and discussion about future therapeutic options. If the subject fails to have a beneficial response following the first month of treatment (Phase 2), the medication will be discontinued and participation in the study will be completed. If the subject elects to discontinue the Brilinta/ticagrelor, despite a beneficial response, participation in the study will be completed.

Outcomes Assessment/Statistical Analysis

Information from this study will be assessed to determine the feasibility of performing a larger randomized, blinded, placebo-controlled multi-center trial. We will assess not only our therapeutic drug response rate in order to estimate a required sample size for the future trial, but also our ability to recruit patients from local referring sources to estimate the time frame of such a trial. Subject compliance rate with use of daily online questionnaires will be determined. Drop-out rates, related to medication side effects will also be assessed.

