1. Statistical Considerations and Analysis Plan:

This is a prospective, open label single-armed trial designed to evaluate the safety and efficacy of Brilinta/ticagrelor (90 mg twice daily) used off-label, in a young healthy population, for the treatment refractory migraine headache. The primary endpoints are:

- Efficacy – Response to treatment defined as a $\geq 50\%$ reduction in chronic headache during a three month period of therapy, compared with baseline.
- Safety – Bleeding events and adverse medication reactions measured over the 3 month treatment period.

Only 40 subjects will be treated in this initial feasibility trial, 20 with episodic migraine, 20 with chronic migraine. We will assess the number of “Responders” in each study group. Responsiveness will be compared with the measured PRU while on therapy. The results of this trial will be descriptive only. It is not anticipated that the number of subjects enrolled will provide statistically analyzable results.

However, if treatment were to be seemingly beneficial, these data could form the foundation for the development of a pivotal randomized, blinded, prospective trial in a larger cohort as mentioned above.

The safety analysis set will include all subjects who receive at least one dose of study medication. This will be the primary analysis set for all safety endpoints which will include major bleeding complications, and adverse drug reactions. Bleeding outcomes, in this younger, healthier cohort will be compared with the previously published PLATO Trial²¹.

Any participant who completes her/his daily headache logs for at least two weeks, but not the full month of the study period, will be classified according to her/his current response status (LOCF), regardless of whether or not he/she completed the required therapy.

2. Analysis of Secondary Endpoints

The secondary endpoints, which will be reported, are as follows:

- Absolute reduction in headache days as a continuous response variable.
- Comparison of the use of rescue medications in the roll-in versus the treatment phase and “successful” interruption of MHA (< 2 hours to resolution) with rescue therapy.
- Non-major bleeding side effects of the medication

STUDY PROCEDURES:

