All potential subjects must have migraine headache documented by a Neurologist. All potential subjects must have a documented RLS by transcranial Doppler (see details above) prior to being a candidate for inclusion into the treatment group. All potential subjects will undergo baseline blood work testing and a urine pregnancy test if indicated. All subjects will take a migraine specific Quality of Life Survey (see below) at the start of the study and at visit #3 and at the conclusion of the continued access phase of the study (if applicable). All subjects will complete a daily headache log (see below), using the REDCap Survey Tool. Each subject will monitor headaches for the first month (28 days) while on her/his baseline medication, and will monitor headaches while also taking Brilinta/ticagrelor 90 mg twice daily for the second month (28-35 days). All subjects will undergo PRU blood testing a minimum of 7 days after the start of the Brilinta/ticagrelor therapy (but prior to its completion). A subject may be eligible for two additional months of Brilinta/ticagrelor therapy, with on-going headache monitoring, if she/he has a positive response to the medication.

STUDY DRUG:

Description:

Brilinta/ticagrelor, the first of a new class of oral anti-platelet agents (cyclopentyltriazolopyrimidines), is a non-competitive, P2Y12 receptor antagonist. Following a loading dose of 180 mg, the drug will be administered in its current FDA approved (2011) dosage of 90 mg twice daily.

[figure not shown]

Figure 1

Approved Uses:

Brilinta/ticagrelor is currently FDA approved as a prescription medicine for patients who:

- Have had a recent heart attack or severe chest pain that happened because their heart wasn't getting enough oxygen
- Have had a heart attack or chest pain and are being treated with medicines or procedures to open blocked arteries in the heart

Formulation/Dosage to be Used:

Brilinta tablets for oral administration contain 90 mg of ticagrelor and the following ingredients: mannitol, dibasiccalcium phosphate, sodium starch glycolate, hydroxypropyl

cellulose, magnesium stearate, hydroxypropyl methylcellulose, titanium dioxide, talc, polyethylene glycol 400, and ferric oxide yellow.

Dose Rationale and Risk/Benefits:

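### Continued access requires a reduction of more than 50% while a Responder needs at least 50%, so a subject at exactly 50% after month 1 is a Responder who is taken off drug

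*Combined protocol and SAP*

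**What the plan says.** All places are in the combined protocol and SAP.

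- **Response.** Working Study Definitions sets the Responder boundary at a 50% or greater "reduction in the average number of monthly headache days during the month of therapy", relative to the subject's own baseline. Primary Study Endpoints uses the same boundary and assigns only those below it to the other class: with less than a 50% "reduction in the number of migraine days, she/he will be considered a Non-Responder".
- **Continuation.** Study Design and Statistical Procedures calls therapy effective under a strict inequality ("> 50% reduction in monthly headache days), the subject could elect to continue therapy for an additional two months"). The Continued Access Phase (Phase 3) paragraph repeats it: "> 50% reduction in the average number of monthly headache days compared with the baseline), she/he will be offered continued access".
- **Consequence of missing the gate.** The same paragraph says: "If the subject fails to have a beneficial response following the first month of treatment (Phase 2), the medication will be discontinued". Participation in the study then ends.
- **Observation windows.** Baseline is 28 days with at least 6 headache days. The Baseline-Monitoring Phase paragraph then says: "The subject will then be treated with Brilinta/ticagrelor for a 28-35 day test period (Phase 2").
- **Analysis plan.** Statistical Considerations and Analysis Plan also uses at least 50%, but as a "reduction in chronic headache during a three month period of therapy, compared with baseline".

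**The concern.** The two boundaries differ only at exactly 50%, but they send that subject in opposite directions: a success on the primary efficacy endpoint, and a failure for the decision to continue. No section reconciles the two or gives a reason for a stricter gate.

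Two things are at stake. First, staff apply the rule at Visit #3 to decide whether a person is offered about two more months of an off-label antiplatelet drug or stops. That decision should agree with the plan's own definition of response. Second, the analysis plan's efficacy period is three months. On that reading, a subject stopped at exactly 50% has month-1 data only. The LOCF rule does not fill the gap, because it is written for subjects who fall short of a full month of logs.

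**Working it through.** The plan gives no figure to reproduce. The check compares the boundaries and then asks how often the boundary case can occur.

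**1. Boundaries.** Let b be baseline headache days (28 days) and t treatment headache days over L days, with L from 28 to 35. Scaled to 28 days, the reduction is 1 − (t × 28/L)/b. Responder: reduction ≥ 50%. Continued access: reduction > 50%. They disagree only when t/L = b/56.

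**2. Can it happen?** With L = 28 the condition is t = b/2, so every even baseline from 6 to 28 can tie (6 to 3, 8 to 4, up to 28 to 14). That is 12 of the 23 possible baselines. With scaling, ties exist at L = 30 (b = 28), 32 (b = 7, 14, 21, 28), 34 (b = 28) and 35 (b = 8, 16, 24), and at no other longer length. In total that is 12 + 1 + 4 + 1 + 3 = 21 of 23 × 8 = 184 pairs of baseline and length.

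**3. Single-subject example.** Take a baseline of 6, a true halving and independent days over 28. The chance of exactly 3 days is C(28,3) × (3/28)³ × (25/28)²⁵ = 0.237. Across even baselines and true reductions of 30% to 70%, this conditional chance runs from about 1% to 24%.

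**4. Expected number in 40.** P(tie) = Σ P(B = b | B ≥ 6) × P(T = t), summed over the tying pairs. All rate inputs are assumptions, because the documents give none:

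- Half the subjects have a true baseline mean spread evenly over 6-14 days, half over 15-27.
- Daily counts are binomial, or beta-binomial with within-period correlation up to 0.10.
- The rate ratio (treatment to baseline) follows one of three patterns, shown as rows below.
- In the scaled column, L is spread evenly over 28-35 days.

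| Rate ratio | 28 v 28 days | 28-35 days scaled to 28 |
|---|---|---|
| Spread evenly from 0 to 1 | 2.7-3.6%; 1.1-1.4 of 40 | 0.55-0.69%; 0.22-0.28 of 40 |
| Exactly 0.5 for everyone (worst case) | 4.0-8.0%; 1.6-3.2 of 40 | 0.84-1.6%; 0.3-0.6 of 40 |
| 70% or 87% respond strongly (ratios from 0 up to 0.2 or 0.3), rest unchanged | 0.5-1.5%; 0.2-0.6 of 40 | under 0.3%; about 0.1 of 40 or fewer |

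The 70% and 87% are taken loosely from the investigators' clopidogrel experience (over 70% in later use; 13/15 = 87%). In the first row, the chance of no tie at all is (1 − 0.036)⁴⁰ = 0.23 to (1 − 0.027)⁴⁰ = 0.33 on the fixed window. With scaling it is (1 − 0.0069)⁴⁰ = 0.76 to (1 − 0.0055)⁴⁰ = 0.80.

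**5. Why the window matters to the gate.** Take a subject with 6 baseline days, 3 headache days by treatment day 28, and a fourth on day 30, the last day of treatment. On the first 28 days the reduction is (6 − 3)/6 = 50%. On the raw count it is (6 − 4)/6 = 33%. Scaled, it is 1 − (4 × 28/30)/6 = 38%. The plan does not say which applies, so the same logs can fall on either side of the boundary.

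**The case against.** The strongest reply is that a continuation gate need not equal an endpoint. The gate is the same in both places where it is quantified, so staff have one numeric rule. A slightly stricter bar before two more months of a drug with bleeding risk is defensible. That is a fair design argument, but the plan does not make it, and it calls exactly these subjects Responders. If the stricter gate is intended, one sentence should say so.

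A second reply is that frequency should not be judged on a 28 v 28 day comparison, because the treatment period may run to 35 days and the definitions speak of an average monthly number. This stands: with scaling, fewer than one tie is expected in every scenario. Both columns are therefore shown.

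Third, the trial is declared descriptive and no analysis of Phase 3 entrants is planned. This also stands and limits the severity.

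Three stronger inferences are tempting and are not supported:

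- **That the mismatch distorts the primary result.** Month-1 status comes from logs completed before the gate is applied, so the Responder count is unchanged.
- **That a subject at exactly 50% is a primary-endpoint success without qualification.** This holds under Working Study Definitions and Primary Study Endpoints. Under the analysis plan's three-month period, response would not yet be settled.
- **That Appendix 1 sets a second, subjective threshold.** Its Visit #3 entry speaks of perceived and clinical benefit, but its later reference to eligibility most naturally points back to the numeric rule, and the Study Design section has logs reviewed at that visit. It is loose wording.

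Nor does the similar looseness over platelet testing ("PRU blood testing a minimum of 7 days after the start of the Brilinta/ticagrelor therapy" in Study Procedures, more than 7 days in the appendices) show that the 50% sign is a slip. It concerns a different procedure.

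**Conclusion.** The inconsistency is real and minor. At exactly 50% after month 1, a subject is a Responder by the protocol's definitions and is taken off drug by its continuation rule. If efficacy were judged over three months, the same subject would have no on-treatment data for months 2 and 3.

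With rate ratios spread evenly from 0 to 1, the expected number is roughly 1 to 1.5 of 40 on a fixed 28-day window. The worst case is about 3, and the number is below 1 if most subjects respond strongly. If 28-35 day periods are scaled to 28, it is well under 1 of 40. These figures rest on assumed headache rates, correlations and treatment lengths. The textual conflict does not depend on them.

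**What to change.** 1. In Study Design and Statistical Procedures and in Continued Access Phase (Phase 3), replace the strict inequality with at least 50%.
2. Compute the log-based status from the first 28 treatment days, to match the 28-day baseline. State the same month-1 window in Working Study Definitions, Primary Study Endpoints, and Statistical Considerations and Analysis Plan. The last must be included, or its three-month efficacy period will still conflict with the other two.

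Make the two changes together. Fixing the window at 28 days while keeping the strict sign would make ties more frequent (in the first row of the table, from 0.22-0.28 to 1.1-1.4 of 40).

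The cost is wording only, with no change to visits, data collected or sample size. There are two consequences. Logs from days 29-35 are still collected but no longer count towards response. Each subject at exactly 50% who elects to continue takes 56-63 more days of drug, which at two tablets a day is 56 × 2 = 112 to 63 × 2 = 126 tablets of 90 mg.
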